6.3. Measures to Minimize Bias: Randomization and Blinding

6.3.1. Allocation to Investigational Product

At Baseline/Day 1, participants will be randomized to 1 of 4 treatment arms for each cohort as shown in [Table 1](#).

Table 1. Treatment Allocation for Intra-Participant Design

Treatment Arm	Cohort ^a	Dosing Regimen	Investigational Product: Lesion 1 ^b	Investigational Product: Lesion 2 ^b	Target Number of Participants to be Randomized
1	1	QD	Crisaborole ointment 2%	vehicle	10
2	1	QD	vehicle	Crisaborole ointment 2%	10
3	1	BID	Crisaborole ointment 2%	vehicle	10
4	1	BID	vehicle	Crisaborole ointment 2%	10
5	2	QD	Crisaborole ointment 2%	vehicle	10
6	2	QD	vehicle	Crisaborole ointment 2%	10
7	2	BID	Crisaborole ointment 2%	vehicle	10
8	2	BID	vehicle	Crisaborole ointment 2%	10

- a. Cohort 1: Ages 12 years and older, Cohort 2: Ages 2 years to under 12 years old.
 b. First, Lesion 1 and 2 will be determined by the investigator at Baseline/Day 1. Then, participants are randomly assigned to one of the treatment arms.

Allocation of participants to treatment groups will proceed through the use of an IRT system. The site personnel (study coordinator or specified designee) will be required to enter or select information including but not limited to the user’s identification (ID) and password, the protocol number, and the participant number. The site personnel will then be provided with a treatment assignment, randomization number, dosing regimen, and dispensable unit (DU) or container number when investigational products are being supplied via the IRT system. The IRT system will provide a confirmation report containing the participant number, randomization number, dosing regimen, and DU or container number assigned. The confirmation report must be stored in the site’s files.

Investigational products will be dispensed at the study visits summarized in the SoA.

Returned investigational products must not be redispensed to the participants.

The study-specific IRT reference manual and IP manual will provide the contact information and further details on the use of the IRT system.

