9.2. Sample Size Determination

For each cohort and for each regimen, a sample size of 16 will have at least 85% power to establish the superiority of crisaborole ointment 2% to vehicle as measured by the change from baseline in TSS between crisaborole treated lesion and the corresponding vehicle treated lesion at Day 15 using paired t -test at 0.025 (one-sided) significance level, assuming the mean of intra-participant difference is 1.8 and standard deviation is 2.2 calculated based

on the pooled results of C3291001 and AN2898-AD-202 studies. In addition, considering that the non-compliance/discontinuation rate during the treatment period is approximately 20%, approximately 20 participants will be enrolled for each regimen, and for each cohort.

In addition, for each cohort, in the inter-participant comparison between crisaborole ointment 2% BID treated lesion and crisaborole ointment 2% QD treated lesion, the sample size of 32 (16 per regimen) and 40 (20 per regimen) will result in a 2-sided 95% confidence interval width of the difference of mean for the change from baseline in TSS will be approximately 1.32 and 1.18, respectively, assuming a common standard deviation is 1.9 based on the pooled results of C3291001 and AN2898-AD-202 studies and the normal approximation.

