**5.1. Hypotheses and Decision Rules**

The primary analysis in each regimen for each cohort will be a superiority test to demonstrate crisaborole ointment 2% is more efficacious than vehicle in the target lesion in participants with mild to moderate AD as measured by change from baseline in TSS between crisaborole treated lesion and vehicle treated lesion. The null hypothesis in each regimen for each cohort is that there is no difference between crisaborole ointment 2% and vehicle, and the alternative hypothesis in each regimen for each cohort is that there is difference between crisaborole ointment 2% and vehicle as measured by change from baseline in TSS at Day 15. In each regimen for each cohort the difference between crisaborole and vehicle in TSS change from baseline at Day 15 is statistically significant if  $p\text{-value} < 0.05$  (two-sided).

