## 6. ANALYSES AND SUMMARIES

### 6.1. Primary Endpoint(s)

#### 6.1.1. Change from Baseline in TSS in Target Lesions at Day 15 (Comparison of Crisaborole vs Vehicle in Each Regimen)

##### 6.1.1.1. Main Analysis

- Estimand strategy: Hypothetical ([Section 2.1](#)).
- Analysis time point: Day 15.
- Analysis set: FAS ([Section 4](#)).
- Analysis methodology: For the intra-participant comparison of crisaborole vs vehicle in each regimen for each cohort, the intra-participant difference of change from baseline in TSS in target lesions between crisaborole and vehicle up to Day 15 will be analyzed using a MMRM that includes the fixed effect of visit specified in [Section 5.2.2](#).
- Intercurrent events and missing data: All efficacy data after discontinuation of treatment will not be considered ([Section 2.1](#)). Observed data will be included in the model, and the missing values will be handled in the model, where the values are assumed to be MAR ([Section 5.3](#)).
- Supporting objective and decision rule: Primary objective, crisaborole is superior to vehicle for the TSS change at Day 15 if the change for crisaborole is greater than for vehicle and if  $p\text{-value} < 0.05$  (two-sided).
- Reporting results:
  - Observed score: The sample size, mean, standard error (SE), standard deviation, median, Q1, Q3, minimum and maximum at baseline and post-baseline visits will be presented for each treatment.
  - Change from baseline: The sample size, mean, SE, standard deviation, median, Q1, Q3, minimum and maximum at post-baseline visits will be presented for each treatment. The least-squares mean of difference and the corresponding SE, 95% CI, p-value will be presented for all post-baseline visits.
  - Figures: 1) Line plots of the mean change ( $\pm$  SE) from baseline to Day 8 and 15 for two treatments (ie, crisaborole vs vehicle) in one figure. Figures will be developed in each regimen for each cohort, separately. In addition, 2) line plots of the mean change ( $\pm$  SE) from baseline to Day 8 and 15 for four treatments (ie, crisaborole BID vs crisaborole QD vs vehicle BID vs vehicle QD) in one figure. Figures will be developed for each cohort, separately.

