## 9. APPENDICES

### Appendix 1. SAS Code

For the intra-participant comparison of crisaborole vs vehicle for each regimen, the following SAS code can be used for analysis of mixed model repeated measure for lesion TSS change from baseline up to Day 15 and other similar continuous endpoint shown in [Section 3](#).

```
proc mixed data=dataset;
  class subjid visit;
  model difference = visit;

  repeated visit/subject=subjid type=un;/*If there is a convergence issue
for type=un, it can be replaced by type=AR(1)*/
  lsmeans visit/cl;
run;
```

Note: difference is the intra-participant difference of change from baseline at each time point up to Day 15 between crisaborole and vehicle.

For the inter-participant comparison of crisaborole BID vs crisaborole QD, the following SAS code can be used for analysis of mixed model repeated measure for lesion TSS change from baseline up to Day 15 and other similar continuous endpoint shown in [Section 3](#).

```
proc mixed data=dataset;
  class subjid regimen visit;
  model difference = regimen visit regimen*visit baseline;

  repeated visit/subject=subjid type=un;/*If there is a convergence issue
for type=un, it can be replaced by type=AR(1)*/
  lsmeans regimen*visit/cl diff cl;
run;
```

Note: difference is change from baseline at each time point up to Day 15 of each regimen.

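### The primary paired-difference model leaves out the randomised lesion position (crisaborole on Lesion 1 or Lesion 2); adding it is a cheap gain in efficiency and robustness

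*SAP*

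**What the plan says.** Protocol 6.3.1 states that "participants will be randomized to 1 of 4 treatment arms for each cohort". Table 1 defines the arms as dosing regimen (QD or BID) crossed with the lesion that receives crisaborole, with a target of 10 participants each. Every regimen-by-cohort cell is therefore split 10:10 by lesion position. The table's footnote fixes the sequence: "First, Lesion 1 and 2 will be determined by the investigator at Baseline/Day 1", and randomisation follows. No rule is given for which lesion becomes Lesion 1.

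Inclusion criterion 6 (Protocol 5.1) requires both lesions to have Lesion ISGA 3. It does not require equal TSS, and bilateral sites are asked for only when possible.

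The primary analysis in SAP 6.1.1.1 takes the within-participant difference in TSS change, which "up to Day 15 will be analyzed using a MMRM that includes the fixed effect of visit". Protocol 9.4.1 and SAP 5.2.2 describe the same model, and SAP Appendix 1 codes it as "model difference = visit". None of them contains a term for arm, lesion position or baseline. The visible sensitivity analyses of the primary endpoint (SAP 6.1.1.2) are the per-protocol set and the pooled cohort, and neither adds such a term.

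**The concern.** The trial randomises by lesion position and then analyses as if it had not. If investigators tend to give the label Lesion 1 to the more prominent or more accessible lesion, the two positions could change by different amounts. ISGA matching does not rule this out: excoriation and lichenification count towards TSS (Protocol Table 3) but do not appear in the ISGA definitions (Protocol Table 2).

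Suppose Lesion 1 improves by d points more than Lesion 2, whatever the treatment. The paired difference then rises by d in one arm and falls by d in the other. A visit-only model treats that spread as residual variation. With equal completers the two shifts cancel in the mean; with unequal completers part of d remains in the treatment estimate.

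SAP 5.1 makes each cell its own test ("In each regimen for each cohort the difference between crisaborole and vehicle in TSS change from baseline at Day 15 is statistically significant" by a two-sided p-value below 0.05), in about 16 evaluable participants and with planned power only just above 85%. At stake is a few points of power, and a small shift in the estimate if completers happen to be unequal.

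**Working it through.** **Inputs.** From Protocol 9.2: "the mean of intra-participant difference is 1.8 and standard deviation is 2.2"; "a sample size of 16 will have at least 85% power"; paired t-test "at 0.025 (one-sided) significance level"; about 20% non-compliance or discontinuation. From Protocol Table 1: 10:10 allocation within each cell. Assumed: d between 0 and 1.5 TSS points, where d is the Lesion 1 minus Lesion 2 difference in change, so the two arm means lie 2d apart. Differences are signed so that positive favours crisaborole.

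**The plan's own figure.** Noncentrality is 1.8/2.2 × √16 = 3.273 on 15 df. The noncentral t gives power of 86.4% at n = 16 and 83.8% at n = 15. The stated power of at least 85% is reproduced, and 16/0.8 = 20 enrolled.

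**Model.** D = τ + s·d + e, with s = +1 if crisaborole is on Lesion 1 and −1 if on Lesion 2. The checks below use Day 15 only.

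**Equal completers (8:8).** The mean of s·d is zero, so the estimate is unbiased and its true standard error stays at 2.2/√16 = 0.55 for every d. Only the estimated SD grows, to about √(2.2² + d²). Entering that inflated SD into a noncentral t would overstate the power loss, so power was simulated. The power columns take 2.2 as the within-arm SD.

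| d | √(2.2² + d²) | Power, visit only | Power, with arm | Two-sided type I error, visit only |
|---|---|---|---|---|
| 0 | 2.20 | 86.3% | 86.0% | about 5% |
| 0.5 | 2.26 | 85.0% | 86.0% | 4.5% |
| 1.0 | 2.42 | 81.0% | 86.0% | about 3.2% |
| 1.5 | 2.66 | 73.9% | 86.0% | 1.9% |

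With arm in the model, two-sided type I error stays at about 5% throughout.

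**If 2.2 already contains the lesion effect.** The within-arm SD is then √(4.84 − d²), that is 2.14 at d = 0.5 and 1.96 at d = 1.0. Power at 8:8 goes from about 87% to 88% at d = 0.5, and from about 88.5% to 93% at d = 1.0, when arm is added.

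**Unequal completers.** The visit-only estimate shifts by d(n1 − n2)/(n1 + n2). At 10:6 that is 4/16 × d = 0.25d, so 0.25 points at d = 1.0 against a planned effect of 1.8. The shift favours crisaborole only if the over-represented arm has crisaborole on the better-responding position; otherwise it works against crisaborole. In the favourable case at d = 1.0, error in that direction rises from 2.5% to about 4.4%, while two-sided error stays at about 4.9%.

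**Random 20% dropout from 10:10.** Mean bias is about zero. Two-sided type I error is 4.9%, 4.6% and 3.7% at d = 0, 0.5 and 1.0. A gap of 4 or more completers occurs in about 4.8% of draws. Power, visit only against with arm, is 85.7% against 84.7% at d = 0, 84.3% against 84.8% at d = 0.5, and 79.7% against 84.6% at d = 1.0.

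**Cost of the term at 10:6 if d = 0.** With equal arm weights the variance factor is ¼(1/10 + 1/6) = 0.0667, against 1/16 = 0.0625. The standard error ratio is √(0.0667/0.0625) = 1.033. Multiplied by the t-quantile ratio 2.145/2.131 = 1.006, it makes the interval about 4% wider. Power falls from about 86.4% to 83.8%.

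**The case against.** The strongest reply is that nothing in the documents shows d to be other than zero. Lesion 1 and Lesion 2 are labels, lesions must match on ISGA, and bilateral sites are preferred. The endpoint is change from baseline, which already removes differences in level. Differences in site or TSS matter here only if they follow the label; otherwise an arm term does not capture them. The planning SD of 2.2 is described as the SD of the intra-participant difference from pooled earlier studies. It may already include any such effect, in which case the planned power has allowed for it. A visit-only model of paired differences also matches the paired t-test used for sample size. All of this stands, and it is why the point is an improvement and not an error.

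A reader might infer two stronger things. The first is that leaving out arm raises the false-positive rate. It does not: with equal completers type I error falls below 5%, and only the estimated error variance is inflated. The second is that unequal dropout biases the result. Labels are set before randomisation, lesion assignment is blinded (Protocol 6.1.1), and a participant who stops treatment leaves with both lesions (Protocol 7.1). Dropout unrelated to arm therefore causes no bias on average. The shift depends on the imbalance that actually arises, and systematic bias would need dropout related to arm.

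The reply is also right that the term costs more than one degree of freedom once completers are unequal.

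**Conclusion.** The omission is real and the planned test is valid on average. This is an optional efficiency and robustness gain. With 2.2 as the within-arm SD and 8:8 completers, adding arm recovers about 1 power point at d = 0.5 and about 5 at d = 1.0. If 2.2 already includes the lesion effect, nothing planned is lost and the term adds about 1 and about 4 points respectively. Under random 20% dropout the balance is closer: the term loses about 1 point at d = 0, gains about half a point at d = 0.5, and gains about 5 at d = 1.0.

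All of this depends on d, which the documents neither state nor imply. The calculations use Day 15 alone. The MMRM would also use Day 8 data from participants who stop later, which should soften the effect of imbalance.

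**What to change.** Add allocation arm (crisaborole on Lesion 1 or on Lesion 2) and arm-by-visit to the intra-participant MMRM in SAP 5.2.2, 6.1.1.1 and Appendix 1 and in Protocol 9.4.1, with LS means weighted equally over the two arms. In Appendix 1:

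`class subjid visit arm; model difference = visit arm arm*visit;`

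with the `repeated` and `lsmeans visit` statements kept. At minimum, keep the visit-only model as primary and prespecify this one as a sensitivity analysis under SAP 6.1.1.2. A stated rule for choosing which lesion is Lesion 1 would also help interpretation.

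Statistical cost if d = 0: about 0.3 power points at 8:8 (interval about 0.6% wider), an interval about 1.4% wider on average under 20% random dropout, and about 2.6 power points (interval about 4% wider) at 10:6.

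Administrative cost: the visit-only model is also in the protocol, and Protocol 9 and SAP 2 require an amendment for a major change to the primary analysis. The primary-model option may therefore need one; a sensitivity analysis could be added in the SAP alone.

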### **6.1.1.2. Sensitivity/Supplementary Analyses**

To support the interpretation of the main analysis the following analyses will be performed.

#### **6.1.1.2.1. Analysis for PPAS**

Except that analysis set is PPAS, the same estimand strategy, analysis time point, analysis methodology, intercurrent events and missing data, supporting objective and decision rule and reporting results as the main analysis ([Section 6.1.1.1](#)) will be used.

#### **6.1.1.2.2. Analysis for Pooled Cohort**

The same analysis as the main analysis ([Section 6.1.1.1](#)) will be conducted for the pooled cohort of cohort 1 and cohort 2.

## **6.2. Secondary Endpoint(s)**

### **6.2.1. Change from Baseline in TSS in Target Lesions at Day 15 (Comparison of Crisaborole BID vs Crisaborole QD)**

#### **6.2.1.1. Main Analysis**

- Estimand strategy: Hypothetical ([Section 2.1](#)).
- Analysis time point: Day 15.
- Analysis set: FAS ([Section 4](#)).
- Analysis methodology: For the inter-participant comparison of crisaborole BID vs crisaborole QD for each cohort, the change from baseline in TSS in target lesions between crisaborole BID and crisaborole QD up to Day 15 will be analyzed using a MMRM that includes the fixed effects of dosing regimen, visit, dosing regimen-by-visit interaction, and baseline value specified in [Section 5.2.2](#).
- Intercurrent events and missing data: All efficacy data after discontinuation of treatment will not be considered ([Section 2.1](#)). Observed data will be included in the model, and the missing values will be handled in the model, where the values are assumed to be MAR ([Section 5.3](#)).
- Reporting results:
  - Observed score: The sample size, mean, SE, standard deviation, median, Q1, Q3, minimum and maximum at baseline and post-baseline visits will be presented for each treatment.
  - Change from baseline: The sample size, mean, SE, standard deviation, median, Q1, Q3, minimum and maximum at post-baseline visits will be presented for each treatment. The least-squares mean and the corresponding SE, 95% CI for each treatment, the difference between the least-squares means of treatments and the corresponding SE, 95% CI, p-value will be presented for all post-baseline visits.

- Figures: Line plots of the mean change ( $\pm$  SE) from baseline to Day 8 and 15 for two treatments (ie, crisaborole BID vs crisaborole QD) in one figure. Figures will be developed for each cohort, separately.

### **6.2.1.2. Sensitivity/Supplementary Analyses**

To support the interpretation of the main analysis the following analyses will be performed.

#### **6.2.1.2.1. Analysis for PPAS**

Except that analysis set is PPAS, the same estimand strategy, analysis time point, analysis methodology, intercurrent events and missing data and reporting results as the main analysis ([Section 6.2.1.1](#)) will be used.

#### **6.2.1.2.2. Analysis for Pooled Cohort**

The same analysis as the main analysis ([Section 6.2.1.1](#)) will be conducted for the pooled cohort of cohort 1 and cohort 2.

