5.1. Inclusion Criteria

Participants are eligible to be included in the study only if all of the following criteria apply:

Age and Sex:

1. Male or female participants ages;
Cohort 1: 12 years and older at the time of consent.
Cohort 2: 2 years to under 12 years old at the time of consent.
 - Refer to Appendix 4 (Section 10.4.1) for reproductive criteria for female participants.

Type of Participant and Disease Characteristics:

2. Participants who are willing and able to comply with all scheduled visits, treatment plan, laboratory tests, lifestyle considerations, and other study procedures.
3. Participants who have confirmed clinical diagnosis of active AD at screening and Baseline/Day 1 according to Hanifin and Rajka criteria and who have at least 6 month history prior to Screening visit and that has been clinically stable for more than 1 month.
4. Participants who have a global ISGA of 2 (mild) or 3 (moderate) at Baseline/Day 1 visit.
5. Participants who have AD lesions on upper limbs, lower limbs or ventral of the body trunk and a body surface area (BSA) covered with AD of at least 1.0% and no more than 30% at Baseline/Day 1, excluding scalp, genitals and groin area. The presence of AD on these areas (scalp, genitals and groin area) is not exclusionary, but will not be included in the calculation for coverage of BSA with AD.
6. Participants who have two lesions of AD at least 3 cm x 3 cm with identical Lesion ISGA = 3 (moderate) for each lesion. These AD lesions must be at least 10 cm apart.

The target lesions must not be on the face, neck, scalp, axilla, genitals, groin area, palms, dorsal of the hands, dorsal of the body trunk and soles. In addition, two AD areas on the same limb must not be selected as the Target Lesions. [Note: When possible, AD areas on the bilateral (left/right) area should have been selected as target lesions].

- Cohort 2: If 0.5%BSA is smaller than 3 cm x 3 cm, 0.5%BSA is acceptable for each of the two AD lesions with identical Lesion ISGA = 3 (moderate) for each lesion.
7. Participants who received any of the following AD treatment regimens are eligible if the following minimum washout criteria are observed:

At least 12 Weeks or 5 half-lives (whichever is longer) prior to Baseline/Day 1:

- Biological drugs.

At least 28 days prior to Baseline/Day 1:

- Systemic (oral/injectable) corticosteroids (Note: use of intranasal/inhaled or ophthalmic corticosteroids for stable medical conditions are allowed);

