6.1.1. Administration

At Baseline/Day 1, the participants who meet Inclusion/Exclusion Criteria will be randomized to one of the regimens, QD or BID, and for each of two target lesion (Lesion 1 and Lesion 2) meeting the inclusion criteria identified by the investigator, the investigational products (crisaborole ointment 2% or vehicle) will be assigned randomly. The sponsor, investigators/study sites and participants will be blinded with respect to which lesion is receiving the crisaborole ointment 2% or vehicle.

	Regimen 1 (QD)	Regimen 2 (BID)
Morning		
Evening	NA	

● Lesion 1
 ▨ Lesion 2

BID: twice daily, NA: not applicable, QD: once daily

In case of Regimen 1 (QD), once daily in the evening throughout the treatment period is acceptable as like as once daily in the morning throughout the treatment period.

For cohort 1, the participants will visit the site at every dosing timing [Regimen 1(QD): once daily in the morning or evening, Regimen 2 (BID): twice daily in the morning and evening] and the investigational products will be applied by the site staff. It may allow that the site staff applies the investigational products at the participant’s home as a backup option upon sponsor’s agreement when the participant is not able to visit the site. For Regimen 2 (BID), dosing interval should be 12±4 hours.

For cohort 2, the parent/caregiver and/or the site staff will apply the investigational products. When the parent/caregiver applies, it will be done with confirmation of the appropriate application by the site staff (directly or via live video chat). When site staff applies, site staff will visit the participant’s home as needed. For Regimen 2 (BID), dosing interval should be 12 ±4 hours.

For regimen 1 (QD), participant will be applied investigational products from Day 1 to Day 14. For regimen 2 (BID), when participant will be applied investigational products from AM in Day 1, the last administration will be PM in Day 14. When participant will be applied investigational products from PM in Day 1, the last administration will be AM in Day 15.

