9.1. Estimands and Statistical Hypotheses

9.1.1. Estimands

The primary estimand of this study is the hypothetical estimand, which estimates the effect as if all participants maintain their randomized treatment. It includes the following four attributes:

- Population: Participants with mild to moderate AD in adults (cohort 1) and pediatrics (cohort 2) as defined by the inclusion and exclusion criteria and are randomized and received at least one of the investigational products;
- Variable: Change from baseline to Day 15 in lesion severity in a continuous outcome measured such as TSS, ISGA and Pruritus assessment in target lesions treated with crisaborole ointment 2% or vehicle in each regimen for each cohort;
- Intercurrent event: All efficacy data after discontinuation of treatment will not be considered;
- Population-level summary: Least-square means of intra-participant difference between crisaborole ointment 2% vs corresponding vehicle in each regimen for each cohort and pooled cohort. Difference in least-square means between crisaborole ointment 2% BID and crisaborole ointment 2% QD for each cohort and pooled cohort.

The primary and secondary efficacy endpoints will be analyzed using this estimand.

CCI

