### **5.2.2. Analyses for Continuous Endpoints**

The continuous endpoints will be descriptively summarized using number, mean, standard deviation, minimum, 1st, 2nd and 3rd quartiles and maximum.

For the intra-participant comparison of crisaborole vs vehicle in each regimen at each time point, a Mixed effect Models for Repeated Measures (MMRM) will be used to derive least-square mean of intra-participant difference and associated 2-sided 95% CI between crisaborole ointment 2% and corresponding vehicle. A MMRM will include the fixed effect of time point (visit or day) and an unstructured variance and covariance matrix will be used to model the dependence among the same participants across different visits up to Day 15. If there is convergence issue for unstructured variance and covariance matrix, first order autoregressive (AR(1)) variance and covariance matrix will be used.

For the inter-participant comparison of regimen 1 vs regimen 2 at each time point, a MMRM will be used to derive difference in least-square means and associated 2-sided 95% CI between regimen 1 and regimen 2. A MMRM will include the fixed effects of dosing regimen, time point (visit or day), dosing regimen-by-time point (visit or day) interaction, and baseline value of the corresponding endpoint and an unstructured variance and covariance matrix will be used to model the dependence among the same participants across different visits up to Day 15. If there is convergence issue for unstructured variance and covariance matrix, AR(1) variance and covariance matrix will be used.

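### The pooled BID vs QD models leave out cohort although randomisation is within cohort, so the pooled intervals may be slightly wider than necessary if the cohorts differ in mean change

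*SAP*

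**What the plan says.** **Pooled analyses.** SAP 6.2.1.2.2 states that the main BID vs QD analysis of TSS "will be conducted for the pooled cohort of cohort 1 and cohort 2". SAP 6.2.3.2 uses the same words for lesion ISGA, where the main analysis includes a BID vs QD comparison.

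**Model.** SAP 5.2.2 specifies: "A MMRM will include the fixed effects of dosing regimen, time point (visit or day), dosing regimen-by-time point (visit or day) interaction, and baseline value". The code in SAP Appendix 1 agrees: "model difference = regimen visit regimen*visit baseline". Neither these places nor SAP 6.2.1.1 and 6.2.3.1 mention cohort as a model term.

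**Randomisation.** Under Protocol 6.3.1, "participants will be randomized to 1 of 4 treatment arms for each cohort". Table 1 there gives 20 QD and 20 BID participants in each cohort.

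**Status.** Protocol 9.1.1 includes the pooled comparison in the population-level summary: BID against "crisaborole ointment 2% QD for each cohort and pooled cohort". Protocol 9.4.1 makes pooling optional, whereas the SAP commits to it. SAP 6.2.1.1 reports a 95% CI and p-value but sets no decision rule for BID vs QD.

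**The concern.** The model was written for one cohort, where a cohort term has no place. Once the cohorts are combined, cohort becomes a design stratum that the model ignores. A difference between cohorts in mean change that baseline does not explain is then counted as residual variation.

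Such a difference is plausible, though not documented. The cohorts differ in age and in who applies the product. Site staff apply it in cohort 1, while Protocol 6.1.1 says: "For cohort 2, the parent/caregiver and/or the site staff will apply the investigational products".

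For TSS, the baseline covariate may absorb part of a gap. For ISGA it cannot. Protocol 5.1 requires two lesions with "identical Lesion ISGA = 3 (moderate) for each lesion", so baseline lesion ISGA is constant among eligible participants.

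What is at stake is the precision of the reported pooled BID vs QD interval. The pooled crisaborole vs vehicle analysis (SAP 6.1.1.2.2) is a separate matter, because a cohort shift common to both lesions of a participant cancels in the within-participant difference.

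**Working it through.** **Inputs.** SD of TSS change: 1.9 (Protocol 9.2, "assuming a common standard deviation is 1.9"). Participants: 20 per regimen per cohort, so 40 per regimen pooled. Cohort gap D in mean change: not in the documents, varied here from 0 to 2 points. The 1.9 is taken as the residual SD within cohort.

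**The plan's own figures.** 1.96 × 1.9 × √(2/16) = 1.317 and 1.96 × 1.9 × √(2/20) = 1.178. These match the 1.32 and 1.18 in Protocol 9.2. They are half-widths, although the protocol calls them widths; this does not affect the present point.

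**TSS without a cohort term.** With equal cohorts and regimen balanced within cohort, a gap D adds D²/4 to the residual variance:

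- SD = √(1.9² + D²/4)
- half-width = 1.96 × SD × √(2/40)
- equivalent n per regimen = 40 × (1.9/SD)²

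For D = 1: SD = √(3.61 + 0.25) = 1.965, half-width = 0.861, equivalent n = 40 × 3.61/3.86 = 37.4.

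| Assumed D (points) | SD | Half-width | Widening | Equivalent n |
|---|---|---|---|---|
| 0 | 1.900 | 0.833 | none | 40 |
| 0.5 | 1.916 | 0.840 | 0.9% | 39.3 |
| 1.0 | 1.965 | 0.861 | 3.4% | 37.4 |
| 1.5 | 2.043 | 0.895 | 7.5% | 34.6 |
| 2.0 | 2.147 | 0.941 | 13.0% | 31.3 |

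A gap of 2.0 would exceed the assumed SD, so it is an outer bound. With a cohort term the half-width stays near 0.833 throughout.

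**ISGA.** The documents give no SD, so only the ratio √(1 + (D/SD)²/4) can be stated. It is 1.008, 1.031, 1.068 and 1.118 for gaps of 0.25, 0.5, 0.75 and 1.0 SD.

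**Simulation of the planned two-visit MMRM.** Settings: 20 per cell, SD 1.9, no true BID–QD difference and 4,000 runs per setting. Assumptions: visit correlation 0.6, and a Day 8 gap half the Day 15 gap. Day 15 half-widths without / with cohort and cohort-by-visit:

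| D | Full data | 20% of Day 15 missing at random |
|---|---|---|
| 0 | 0.850 / 0.850 | 0.912 / 0.913 |
| 0.5 | 0.854 / 0.846 | 0.918 / 0.912 |
| 1.0 | 0.878 / 0.849 | 0.943 / 0.915 |
| 2.0 | 0.960 / 0.847 | 1.029 / 0.913 |

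The widening is about 1%, 3% and 13% for gaps of 0.5, 1 and 2 points, as in the formula. With 20% missing and D = 1, the two models' estimates differed by 0.000 on average (SD 0.047).

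**Direction of the error.** A Day 15 ANCOVA simulation with an assumed baseline correlation of −0.4 and 20 per cell gave almost the same spread of estimates with and without cohort (0.389 and 0.390 at D = 1). Balance within cohort already keeps the gap out of the estimate's sampling error, but the model without cohort still counts it in the standard error. Coverage was 96% at D = 1 and 98% at D = 2 without the term, against about 95% with it. The test is therefore conservative. The widening in this setting was 4% and 16%, because baseline adjustment shrinks the residual SD to 1.9 × √(1 − 0.16) = 1.74 and the gap is larger relative to it.

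**The case against.** The strongest objection is that nothing depends on this. The pooled runs are supplementary, BID vs QD has no decision rule, and Protocol 2.1 describes regimen selection as descriptive and by age group. At gaps of 0.5 and 1 point the half-width grows by 0.007 and 0.028 on a 0–12 scale. All of this stands and limits the point to minor.

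The gap is also entirely assumed, and Protocol 6.1.1 weakens one mechanism for it, since caregiver application is to be confirmed by site staff directly or by live video. That is fair. It does not remove the age difference, and SAP 6.5.3 plans to summarise unconfirmed applications in cohort 2.

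The percentages depend on how much baseline explains. This is true in both directions: baseline may absorb part of a TSS gap, but it also lowers the residual SD, which gave 4% and 16% in place of 3.4% and 13%.

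Simulated type I error rates are noisy. At D = 1 with full data they were 4.0% without the term and 4.6% with it, with a Monte Carlo standard error of about 0.35 percentage points on a 5% rate. The conservatism rests better on the variance argument than on those rates.

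Finally, the loss is one of precision alone only while evaluable numbers stay balanced. If losses differ by cohort and regimen together, the model without cohort can also shift the estimate. That is a further reason to include the term.

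**Conclusion.** The concern holds as a minor point. The pooled BID vs QD models for TSS and lesion ISGA omit a stratum within which participants were randomised, and if the cohorts differ in mean change the reported intervals are wider than they need be. For TSS the cost is 0.9% at an assumed 0.5-point gap, 3.4% at 1 point and 13% at 2 points. It is nil at no gap. For ISGA it is 0.8% to 11.8% for gaps of 0.25 to 1.0 SD.

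These figures assume equal cohorts, regimen balanced within cohort and, for TSS, a within-cohort residual SD of 1.9. There is no expected bias at the planned 20 per cell and no inflation of false positives. The per-cohort results that inform the choice of regimen are unaffected. This is an inexpensive improvement and does not threaten a conclusion.

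**What to change.** In SAP 6.2.1.2.2, and for the BID vs QD part of 6.2.3.2, state that the pooled model adds cohort and cohort-by-visit as fixed effects. In the Appendix 1 code for pooled runs, put `cohort` in the class statement and `cohort cohort*visit` in the model statement. Specify this before unblinding, so that it cannot look driven by the data.

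Show the per-cohort BID–QD estimates and intervals, already produced under 6.2.1.1 and 6.2.3.1, beside the pooled estimate as a descriptive check. Do not make pooling conditional on a regimen-by-cohort interaction test: with 20 per cell its standard error is about 1.9 × √(4/20) = 0.85 TSS points, too large to be informative.

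The pooled crisaborole vs vehicle analysis in 6.1.1.2.2 need not change. It would help to say there whether the p<0.05 rule of 6.1.1.1 applies to the pooled run.

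The cost is one SAP sentence, two model terms and about one between-participant degree of freedom. At no gap the simulated half-width is 0.850 either way with full data, and 0.912 without against 0.913 with the terms when 20% of Day 15 values are missing. The per-cohort analyses stay as they are.
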